5. STUDY POPULATION

5.1.1. Total Vaccinated Cohort

The total vaccinated cohort (TVC) will include all subjects who received at least one dose of vaccine (TVC for booster safety analysis will include all the subjects who received the booster dose):

- A safety analysis based on the TVC will include all vaccinated subjects.
- An immunogenicity analysis based on the TVC will include all vaccinated subjects for whom immunogenicity data are available.

The TVC analyses will be performed per investigational vaccine actually administered at the first dose.

The analysis of safety will be performed on the TVC.

5.2. Cohort for analysis of the immunogenicity-fever score

The analysis cohort for combined immunogenicity and safety of the two-dose primary series will include all subjects in the ATP cohort for immunogenicity analysis at Day 42 for whom temperature measurements are available during the first 3 days after both vaccine doses 1 and 2.

Subjects without immunogenicity results at Day 42 or for whom one or more daily temperature measurements are missing during the first 3 days after either vaccine dose [dose 1 or dose 2] will be excluded from the immunogenicity/fever index calculation for the primary series.

The list of applicable elimination codes for each cohort can be found in the study specific form FORM-9000036402-13 Criteria for eliminating subjects from the analyses and filled in CARS.

Cohort	Elimination codes	Eli Type
ATP cohort for Day 42 analysis of the immunogenicity	1030;1040;1050;1060;1070;1080; 1090; 2010; 2040; 2050; 2060; 2070; 2080; 2090; 2100; 2500.	PR
ATP - Day 385 (Persistence)	1030;1040;1050;1060;1070;1080 ; 1090; 2010; 2040; 2050; 2060; 2070; 2080; 2090; 2100; 2500.	PE
ATP Day 392 post-booster dose.	1030;1040;1050;1060;1070;1080; 1090; 2010; 2040; 2050; 2060; 2070; 2080; 2090; 2100; 2500.	MA (including PR)

6. STATISTICAL METHODS

6.1.1. Analysis of demographics

The analysis of demography will be performed on the TVC and on the ATP for immunogenicity.

Demographic characteristics (age at first study vaccination in months; gender; ethnicity) of all subjects will be tabulated by study group and overall using descriptive statistics:

- Frequency tables will be generated for categorical variables such as ethnicity.
- Mean, range, median, and standard deviation will be provided for continuous data such as age.

The distribution of subjects enrolled among the study sites (center) will be tabulated as a whole and per group.

In addition, the following table will be performed for Clinical Trial Register (CTR) posting:

- Percentage of Enrolled subjects by country will be tabulated by group and pooled vaccine groups.

6.1.2. Analysis of immunogenicity

The primary analysis will be based on the ATP cohort for analysis of immunogenicity. If, in any study group, the percentage of vaccinated subjects with serological results excluded from the ATP cohort for analysis of immunogenicity is 5% or more, a second analysis based on the TVC will be performed to complement the ATP analysis.

6.1.2.1. Immunogenicity/fever indices (Co-primary objectives)

An analysis of covariance model (ANCOVA) will be fitted on the \log_{10} transformed HI and MN antibody responses at Day 42, with the vaccine group as a fixed independent variable, adjusted by the \log_{10} transformed pre-vaccination titer and age.

For **vaccine homologous** HI and MN separately, an immunogenicity index (D_{GMT}) will be constructed using a desirability function based on the computed GMT group ratio (alternative dose regimen to reference = 1.9 μ g HA with AS03_B) and the 95% CI.

D_{GMT} will be the LL of the 95% CI for GMT group ratio

- If the LL of the 95% CI for GMT group ratio is less than 0.25 (i.e., 4- fold less than that of the reference group), then $D_{GMT} = 0$.
- If the LL of the 95% CI for GMT group ratio is greater than 1 (comparison group has higher GMT value than the reference group), $D_{GMT} = 1$.
note $D_{GMT} = 1$ for the reference group

The fever index (D_R) will be calculated according to body temperature measurements performed from Days 0-2 after each dose

- Any temperature $< 38^{\circ}\text{C}$ (100.4 F) will be assigned a value of 0. Any temperature $> 40.5^{\circ}\text{C}$ will be assigned a value of 40.5).
- The highest possible temperature value per subject is 243 (6 x 40.5°C ; i.e. for 3 days after dose 1 and dose 2);
- The lowest possible temperature value per subject is 0 (all measurements $< 38.0^{\circ}\text{C}$ (100.4 F) for 3 days after dose 1 and dose 2).
- For each subject, a temperature index will be constructed as follows: (243 minus the sum of recorded temperature values for 3 days after dose 1 and dose 2)/243. The average temperature measurement for each vaccine group will be calculated as the D_R . A lower index value D_R indicates a less desirable regimen in terms of reactogenicity.

An immunogenicity-fever index (D) at Day 42 will be computed for each group

$$D = \sqrt{D_{GMT} \times D_R}$$

This index (D) will range between 0 and 1 (0 = not desirable; 1 = highly desirable) and the same weight (0.5) is assigned for immunogenicity index and reactogenicity (fever) index.

Two immunogenicity-fever indices will be separately calculated for HI and MN **assay against vaccine-homologous virus**. Each will be used to rank the different dosing regimens as a tool to guide dosing regimen selection.

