### 1.2. Rationale for the study

GSK's AS03-adjuvanted monovalent pandemic H5N1 influenza program in children includes three clinical studies (two uncontrolled, one controlled) using its Dresden manufactured D-Pan H5N1 vaccine and one placebo-controlled clinical study using its Quebec manufactured Q-Pan H5N1 vaccine.

In the first D-Pan H5N1 trial, 3.75 or 1.9 µg of **hemagglutinin (HA)** antigen mixed with 2 concentrations of adjuvant, AS03A and AS03B, were evaluated. An H5N1 vaccine containing 1.9 µg of HA combined with AS03B (half the adult dose of 3.75 µg HA+ AS03A), administered as a 2-dose regimen 21 days apart, was chosen for further **clinical** development in children. This regimen has been shown to elicit strong immunogenicity with an acceptable safety profile. *(Amended: 27-MAR-2017)*

In some subsequent clinical studies of D-Pan H5N1 vaccines containing 1.9 µg HA antigen and AS03B, children below 6 years of age showed an increase in reactogenicity (especially fever) after a second (or third) dose. In the clinical trial of Q-Pan H5N1 vaccine containing 1.9 µg HA and AS03B, increased incidences of fever after a second dose were not observed in 607 children, 6 months to 17 years of age. However the overall incidence of local solicited and unsolicited symptoms 7 days after vaccination increased relative to saline placebo. As known from adjuvanted vaccines, there was an increase in solicited local and some general AEs within 7 days post vaccination in **H5N1** vaccine recipients compared to placebo recipients. *(Amended: 27-MAR-2017)*

The aim of this dose ranging study is to assess whether reactogenicity can be reduced while maintaining adequate immunogenicity in a pediatric population. This study will either confirm that the current pediatric formulation represents an acceptable balance between immunogenicity and reactogenicity, or will suggest that the adjuvant or antigen dose, or both, could be modified.

Study Flu Q-Pan-023 is part of the clinical development plan for D-H5N1 vaccine supporting both *Prepandrix* and *Adjupanrix* licenses in EU and is included in the current approved Paediatric Investigation Plan (PIP) of both products.

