### 1.3. Rationale for the study design

This study will assess the balance between immune responses and adverse effects associated with different amounts of AS03 adjuvant and Q-Pan H5N1 antigen in combination. In previous pediatric studies, 1.9 µg HA combined with AS03B was highly immunogenic and had an acceptable safety profile [Kosalaraksa, 2015]; it has therefore been defined as the reference dose for this study. Alternative doses will include 0.9 µg, 1.9 µg, or 3.75 µg HA in combination with AS03C (approximately one-fourth the adult dose of AS03) or 3.75 µg HA antigen in combination with AS03D (approximately one-eighth the adult dose of AS03).

The schedule for the priming regimen in this study (2 doses, 21 days apart) is consistent with the schedule used in all prior pediatric studies.

The study will plan to enrol 37 children per group to achieve 34 evaluable subjects per group with an overall target of 185 children. Power calculations are given in Section 10.3.

Experience with D-Pan H5N1 vaccines suggests that fever, in addition to being objectively measurable, is a relevant parameter indicative of reactogenicity in children below 6 years of age. Accordingly, this study will use fever (defined as a body temperature  $\geq 38^{\circ}\text{C} / 100.4^{\circ}\text{F}$ ) by any route; axillary is preferred in this study) within 3 days after each dose to assess the balance between reactogenicity and immunogenicity. This will be evaluated via immunogenicity-fever indices constructed using Day 42 immune response either by hemagglutination inhibition (HI) assay or by microneutralization (MN) assay and reactogenicity as assessed by fever score.

The 6 – 35 month age group, which has had both the highest rates of fever and the highest post-vaccination antibody titers in previous clinical trials, will be studied. Reactogenicity and immune response in this age group will inform dose selection across the entire pediatric population.

For a pandemic vaccine, which might have to protect against a second or third wave of H5N1 infections, the quality and persistence of the immune response after priming are important parameters.

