6.1.3. Analysis for safety

- Safety data will be analyzed based on the TVC.
- Analysis will be of subject incidence rates of solicited and unsolicited adverse events (AEs), by solicited local and general AEs terms, and, for unsolicited AEs, by MedDRA preferred term and system organ class. Safety data will be summarized for all subjects by treatment group. The incidence of solicited local and general AEs occurring during 7 days after vaccination will be tabulated with exact 95% CI for each treatment group. The same calculations will be performed for AEs of any

intensity, those with intensity Grade ≥ 2 , and those with intensity of Grade 3, as well as for solicited general events assessed as related to vaccination. All solicited local AEs are considered to be related to vaccination.

- The percentage of subjects with at least one report of an unsolicited AE classified by MedDRA (System Organ Class and Preferred Term) 21 days after each primary vaccination will be tabulated with exact 95% CI for each treatment group. The same tabulation will be performed for Grade 3 unsolicited AEs and for unsolicited AEs that are considered by the investigator to be possibly or probably related to vaccination.
- The percentage of subjects with at least one report of an unsolicited AE classified by MedDRA (System Organ Class and Preferred Term) 30 days after the booster vaccination will be tabulated with exact 95% CI. The same tabulation will be performed for Grade 3 unsolicited AEs and for unsolicited AEs that are considered by the investigator to be possibly or probably related to vaccination.
- The proportion of subjects who begin at least one new concomitant medication during the first 42 days after primary vaccination will be calculated with 95% CI.
- MAEs, AESIs, SAEs, and pIMDs will be summarized through the entire study period. In addition, serious AEs and withdrawals due to AE(s) will be described in detail.

The pIMD listings will include pIMDs reported by the Investigator and those identified from the clinical database search using a list of pre-specified pIMD PTs.

The AESIs listings will include AESIs identified from the clinical database search using a list of pre-specified AESIs PTs and SMQs. The AESIs will include the events listed below and the MedDRA PT or SMQ used to identify reports of these events is provided in parentheses:

- Anaphylaxis (narrow SMQs “Anaphylactic reaction” and “Angioedema”)
- Bell’s palsy (MedDRA PT “VIIth nerve palsy”)

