7.4. Interpretation of analyses

In this study, all the comparative analyses will be descriptive with the aim to rank alternative dosing regimens with respect to immunogenicity and reactogenicity at Day 42, persistence at Day 385, and anamnestic response to unadjuvanted antigen booster dose at Day 392. In order to evaluate all the effects at the same scale (values between 0-1), a persistence parameter and a booster effect parameter will be calculated for HI and MN:

- Persistence index = $(MGI - 4)/MGI$ for each group.
- Boostability index = $(MGI - 4)/MGI$ for each group.

If the MGI value is less than 4, the index will be set to 0, the immunogenicity- fever, persistence and boostability indices will be ranked for each vaccine group.

Given the complexity of possible outcomes, an algorithm for dose selection will **not** be proposed.

Dose selection will be based on Day 42 immunogenicity and fever as key indicator of reactogenicity, persistence of the immune response and anamnestic response to unadjuvanted antigen as well as any additional safety concerns. Additional practical matters related to the estimated incremental benefit versus the complexity of a pediatric specific dosing regimen, should it not be a fraction of the adult dose, will also be weighed for dose selection as this could lead to increased complexity from a manufacturing and delivery perspective in a pandemic response setting.

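### Does the fever index D_R miss a regimen that makes fevers milder, because it is close to a count of febrile days?

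*SAP*

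**What the plan says.** SAP 6.1.2.1 (Amendment 2), in the same terms as Protocol 10.6.2.1, builds the fever index from six daily temperatures, Days 0-2 after each priming dose. Readings below 38 °C count as 0. Readings from 38 °C up enter as recorded, capped at 40.5. The subject index is "243 minus the sum of recorded temperature values for 3 days after dose 1 and dose 2)/243". The next sentence reads "The average temperature measurement for each vaccine group will be calculated as the" D_R, and a lower value is less desirable. D is the square root of D_GMT × D_R and is used to rank the regimens.

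On purpose, Protocol 1.2 sets out to "assess whether reactogenicity can be reduced while maintaining adequate immunogenicity in a pediatric population". Protocol 1.3 says "this study will use fever (defined as a body temperature" of at least 38 °C, within 3 days of each dose, to judge the balance with immunogenicity. On use, SAP 7.4 states "Dose selection will be based on Day 42 immunogenicity and fever as key indicator of reactogenicity", together with persistence, booster response and any additional safety concerns. It also says "Given the complexity of possible outcomes, an algorithm for dose selection will" not be proposed.

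**The concern.** An index built from recorded temperatures, with a cap at 40.5 °C, looks as if it measures how high fevers run. It barely does. Because afebrile days score 0 and not 38, almost all of a febrile day's penalty comes from crossing the threshold. In a group of 34, eight children with one day at 38.0 °C give a worse D_R than seven children with one day at 40.5 °C or more.

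Elsewhere the plan treats height as meaningful: Protocol Table 22 uses both 38 °C and 38.5 °C, and SAP 7.1.3.2 grades temperature 0-4. If less adjuvant made fevers milder without making them rarer, D_R would hardly move. Since the regimens are weighed by judgement and not by an algorithm, a real gain in tolerability could be overlooked. A second D_R on the 0-4 grades, shown beside the stated one, would seem a cheap safeguard.

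**Working it through.** **1. The plan's own figures.** Maximum sum per subject: 6 × 40.5 = 243, as stated. Protocol Table 22: 1 − (1 − 0.224)^34 = 0.9998 and 1 − (1 − 0.107)^34 = 0.9787, matching the stated ≥99.9% and 97.9%.

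**2. Cost of one febrile day**, min(T, 40.5)/243:
- 38.0 °C: 38/243 = 0.1564
- 40.5 °C or more: 40.5/243 = 0.1667
- ratio 40.5/38 = 1.066; share due to crossing 38 °C at least 38/40.5 = 93.8%

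Group of 34: eight at 38.0 °C give 1 − 8 × 38/(34 × 243) = 0.9632; seven at 40.5 °C give 1 − 7 × 40.5/(34 × 243) = 0.9657. So D_R is close to a febrile-day count. Mild fever is not ignored: it carries nearly the full daily cost.

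**3. The case in which this hurts.** The comparator is a graded index, (24 − sum of six grades)/24. Assume the Table 22 rates (given for 7 days) hold in the 3-day window and n = 34, and let febrile time run from one day after one dose to two days after each. If every fever of 38.5 °C or more becomes a low fever and incidence at 38 °C stays exactly the same, the milder regimen ranks higher on D_R in 54-56% of simulated pairs (stated) against 83-96% (graded). If instead incidence is halved, the order reverses: 89-96% stated, 84-94% graded.

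**4. The case left out: temperatures fall generally.** Fit an exponential tail above 38 °C to the two protocol rates. The fraction of fevers at or above 38 + d is (10.7/22.4)^(d/0.5) = 0.4777^(d/0.5). A uniform drop of d therefore leaves this incidence:
- 0.2 °C: 22.4% × 0.744 = 16.7%
- 0.3 °C: 22.4% × 0.642 = 14.4%
- 0.5 °C: 22.4% × 0.478 = 10.7%

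The last line follows from the two protocol rates directly, whatever the shape of the tail. Under an exponential tail the temperatures of the remaining fevers keep their distribution. The expected loss 1 − D_R thus shrinks by the same factor on both scales, and the scale with less relative noise separates the regimens better. Simulated share of pairs in which the milder regimen ranks higher on D_R (same duration patterns, ties not counted as wins):

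| Drop | Stated D_R | Graded D_R |
|---|---|---|
| 0.2 °C | 72-81% | 67-78% |
| 0.3 °C | 80-90% | 75-87% |
| 0.5 °C | 90-98% | 86-96% |

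At half the protocol rates the stated version also led in every case.

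**5. Effect on D.** With SD 0.60 (Protocol 10.3), one standard error of the log10 GMT difference between two regimens is 0.60 × √(2/34) = 0.1455, a factor of 1.40 on the ratio and √1.40 = 1.18 on D. Take one febrile day after each dose, 11.7% of children at 38.2 °C and 10.7% at 39.5 °C, and lower the latter to 38.2 °C. Stated D_R goes from 0.9284 to 0.9296 (D × 1.0006) and graded D_R from 0.9635 to 0.9813 (D × 1.009). Either shift is small beside that noise.

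**6. What is already reported.** SAP 4.2 lists percentage, intensity and duration of each solicited general event as endpoints. SAP 6.1.3 tabulates any grade, Grade 2 or higher and "those with intensity of Grade 3, as well as for solicited general events" judged related. SAP 7.1.3.4 defines duration as the number of days with the symptom, and SAP 7.3 sets the format for its summary statistics. Febrile days and fever height therefore both have planned displays.

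**The case for a change.** The best argument for a graded column is that these safety displays do not match the index. They cover 7 days in the total vaccinated cohort, while D_R covers Days 0-2 in the Day 42 ATP subjects "for whom temperature measurements are available during the first 3 days after both vaccine doses 1 and 2". SAP 6.1.3 also names Grade 3 where the temperature scale runs to 4. No display in the SAP text shows severity in the index's own cohort and window, and if incidence at 38 °C really were unchanged, D_R would be close to uninformative about severity.

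All of that is accurate, but it does not make a defect. The cohort difference is roughly 37 against 34 children per group (Protocol 1.3). The tables, figures and listings annex is not among the documents, so the absence of such a display is not established. Protocol 1.3 says dose selection also weighs safety concerns that the indices do not capture, and one vaccine-related fever above 40 °C already meets holding rule 1e in Protocol Table 20, so extreme fevers do not depend on D_R to be noticed. The grade steps are themselves a convention: one day at 39.0 °C would count as three days at 38.0 °C.

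The phrase "The average temperature measurement for each vaccine group will be calculated as the" D_R is loosely worded. It follows the definition of a subject index between 0 and 1 and precedes the statement that lower is worse, so only the mean of the subject indices fits. That is editorial.

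**Conclusion.** The concern does not hold. D_R is nearly a febrile-day count (6.6% between the lowest and highest febrile day), and that agrees with the protocol's definition of the construct as fever at 38 °C or more. No passage promises weighting by height. The supposed blindness is confined to fevers that become milder with no child or day falling below 38 °C, a pattern nothing in the documents makes likely. When temperatures fall generally, the stated index ranks the milder regimen correctly slightly more often than the graded one, by about 2 to 5 percentage points at the matching ends of the ranges. Grading is thus a trade-off and not a correction, and it would leave the prespecified D unchanged.

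This rests on the 7-day fever rates applying to the 3-day window in full or by half, an exponential tail through two points, and assumed durations of one or two febrile days per dose. The arithmetic of the index and the fall from 22.4% to 10.7% with a 0.5 °C drop in all temperatures need no tail or duration assumption.

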**Synopsis Table 2 Study groups and treatment foreseen in the study**

Treatment name	Vaccine/Product name (Formulation)	Study Groups				
		190_B	090_C	190_C	375_C	375_D
1.9 mcg H5N1 HA + AS03B	FLU-Q-PAN (A/Indonesia/05/2005 H5N1 HA, 15 µg/mL)	●				
	AS03A (AS03 47.44 mg/mL, final vaccine dose contains 5.93 mg tocopherol)	●				
0.9 mcg H5N1 HA + AS03C	FLU-Q-PAN (A/Indonesia/05/2005 H5N1 HA, 15 µg/mL)		●			
	AS03A (AS03 47.44 mg/mL, final vaccine dose contains 2.97 mg tocopherol)		●			
1.9 mcg H5N1 HA + AS03C	FLU-Q-PAN (A/Indonesia/05/2005 H5N1 HA, 15 µg/mL)			●		
	AS03B (AS03 23.72 mg/mL; final vaccine dose contains 2.97 mg tocopherol)			●		
3.75 mcg H5N1 HA + AS03C	FLU-Q-PAN (A/Indonesia/05/2005 H5N1 HA, 30 µg/mL)				●	
	AS03B (AS03 23.72 mg/mL; final vaccine dose contains 2.97 mg tocopherol)				●	
3.75 mcg H5N1 HA + AS03D	FLU-Q-PAN (A/Indonesia/05/2005 H5N1 HA, 30 µg/mL)					●
	AS03C (AS03 11.86 mg/mL; final vaccine dose contains 1.48 mg tocopherol)					●
3.75 mcg H5N1 HA	FLU-Q-PAN (A/Indonesia/05/2005 H5N1 HA, 15 µg/mL)	●	●	●	●	●

- Vaccination schedule:
  - All subjects are to receive an AS03 adjuvanted H5N1 vaccine given as a two-dose primary series at a 21 day interval.
  - All subjects are to receive a 3.75 µg HA, un-

adjuvanted H5N1 vaccine as a booster dose at Day 385.

- Control: None
- Treatment allocation: Randomization will be 1:1:1:1:1 with 37 subjects per group.
- Blinding: observer-blind

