**Table 21 Lower limit of 95%CI for GMT ratio of vaccine group to the reference group 21- days after second vaccination**

	log GMT standard deviation				
	0.50	0.55	0.60	0.65	0.70
GMT ratio	0.25	0.14	0.13	0.13	0.12
	0.29	0.16	0.16	0.15	0.14
	0.34	0.19	0.18	0.17	0.16
	0.4	0.23	0.21	0.20	0.19
	0.5	0.28	0.27	0.25	0.24
	0.67	0.38	0.36	0.34	0.32
	1	0.57	0.54	0.51	0.48

Assumed non-evaluable rate is less than 10%, with a sample size of 34 evaluable subjects per group and SD (log value)=0.60, the LL of 95%CI for the GMT ratio would be 0.25 if the point estimate of GMT ratio of vaccine group to the reference group is 0.5 (50% of GMT value deduction).

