7.2. Methodology for computing CI

All CI will be 2 sided 95% CI.

- The exact 95% CIs for a proportion within a group will be calculated from Proc StatXact [Clopper CJ, Pearson ES, 1934].
- The 95% CIs for GMT are obtained within each group separately. The 95% CI for the mean of lot-transformed titer is first obtained assuming that log-transformed titers are normally distributed with unknown variance. The 95% CI for the GMT is then obtained by exponential-transformation of the 95% CI for the mean of log-transformed titer.
- The group GMT ratio will be obtained using an ANCOVA model on the logarithm- transformed titers. The ANCOVA model will include the vaccine group as fixed effect and the pre-vaccination \log_{10} titer and, age as regressor. The GMT ratio and its 95% CI will be derived as exponential-transformation of the corresponding group contrast in the model.

7.3. Data presentation description:

The following decimal description from the decision rules will be used for the demography, immunogenicity and safety/reactogenicity.

Display Table	Parameters	Number of decimal digits
Demographic characteristics	Mean, median age	1
Demographic characteristics	SD (age)	1
Immunogenicity	Ratio of GMT	2
Reactogenicity	Mean, Min, Q1, Median, Q3, Max for duration	1
All summaries	% of count, including LL & UL of CI	1
All summaries	% of ratio, including LL & UL of CI	1

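### Regimens are ranked on D and on the persistence and boostability indices, but no interval or rank uncertainty is carried to these indices

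*SAP*

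**What the plan says.** SAP 6.1.2.1 (and Protocol 10.6.2.1) builds D as the square root of D_GMT times D_R. For the immunogenicity part, "D_{GMT} will be the LL of the 95% CI for GMT group ratio", set to 0 if that limit is below 0.25 and to 1 if it is above 1; the reference group is given 1. D_R is a group mean of a per-child temperature score. Of the HI and MN versions of D, the SAP says: "Each will be used to rank the different dosing regimens as a tool to guide dosing regimen selection".

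SAP 7.4 adds two indices, each (MGI − 4)/MGI and set to 0 when MGI is below 4. It states that the "persistence and boostability indices will be ranked for each vaccine group", together with the immunogenicity-fever index.

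SAP 7.2 says "All CI will be 2 sided 95% CI" and describes methods for proportions, GMTs and the GMT ratio. SAP 6.1.2.2 and 6.1.2.3 plan 95% CIs for the MGIs, and SAP 6.1.3 plans exact CIs for solicited events, which include fever. No interval, standard error, rank probability or rule for indistinguishable regimens is given for D, D_R, the two MGI indices or the ranks.

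**The concern.** The output of the co-primary index analysis is an ordering of five regimens. With about 34 evaluable children per group, regimens that do not differ will nearly always receive different index values and so be ordered. A reader of the ranking cannot tell a real advantage from sampling noise without the precision of the index or of the difference between two indices.

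D_GMT looks like an answer because it is itself a confidence limit. But it limits each alternative's ratio to the reference, and says little about whether one alternative differs from another. Because the reference is fixed at 1, it also places the alternatives and the reference on unequal footing within the same ranking.

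**Working it through.** **Inputs.** Five groups, allocated equally: "Randomization will be 1:1:1:1:1 with 37 subjects per group" (Protocol synopsis). Precision: "with a sample size of 34 evaluable subjects per group and SD (log value)=0.60", with SD 0.50 to 0.70 across Table 21. Planning fever incidence is 22.4% (Table 22). Index rules are those of SAP 6.1.2.1.

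**The plan's own figure.** Protocol 10.3 states that "the LL of 95%CI for the GMT ratio would be 0.25 if the point estimate of GMT ratio" is 0.5. The formula is LL = ratio × 10^(−t × SD × √(2/n)). With t = 2.0345 (33 df), SD 0.60 and n = 34:

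- 2.0345 × 0.60 × √(2/34) = 0.296, and 10^(−0.296) = 0.506
- 0.5 × 0.506 = 0.253

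This matches 0.25, and the same formula reproduces all 28 legible cells of Table 21.

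**The factor under the planned ANCOVA.** One pooled variance over five groups gives about 160 df and t = 1.975. The multiplier is then 10^(−1.975 × 0.60 × 0.2425) = 0.52 at SD 0.60 (0.58 at SD 0.50, 0.46 at SD 0.70). With equal group sizes and no covariates, the multiplier is the same for every alternative in a given trial. Ordering the four alternatives by lower limit is then the same as ordering them by point estimate. Unequal groups and covariates would cause only small departures.

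**The tilt toward the reference.** Assume every regimen is identical, 22.4% of children are febrile, and each has 1.5 febrile days at 38.5 °C.

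- D_R = 1 − 0.224 × 1.5 × 38.5/243 = 0.947
- Reference: D = √(1 × 0.947) = 0.97
- An identical alternative with an observed ratio of 1: D = √(0.516 × 0.947) = 0.70

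**Simulation.** 20,000 trials of five groups of 34, pooled variance, no baseline-titre or age covariates, SAP rules for D. Fever assumptions are as above except where stated.

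| Scenario | SD 0.50 | SD 0.60 | SD 0.70 |
|---|---|---|---|
| Four identical alternatives at ratio 1: median top-to-bottom gap in D | 0.14 | 0.165 | 0.20 |
| One alternative with 25% higher GMT than the other three, 15% fever in all four: ranked first among the four (25% by chance) | 58–59% | 53–54% | 49% |
| All four alternatives truly at ratio 0.5: some score D = 0 and others do not | 51% | 59% | 58% |

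At SD 0.60, one alternative's D at true ratio 1 has a 95% sampling range of about 0.50 to 0.96. With all five regimens identical, the reference ranks first in about 95 to 96% of trials, against 20% by chance. It still ranks first in about 90% if the alternatives cause no fever at all (run with 1 febrile day per febrile child).

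The fever assumption matters little: the SD of D_R is only about 0.01 to 0.02, and at SD 0.60 the median gap is 0.166 with 1 febrile day and 0.163 with 2.

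**MGI indices.** The documents give no SD for the log10 fold-rise; 0.4 to 0.6 is assumed. At MGI 8, SD 0.5 and n = 34:

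- MGI limits are 8 × 10^(±2.0345 × 0.5/√34), which is 5.35 and 11.95
- Index = (8 − 4)/8 = 0.50, with limits (5.35 − 4)/5.35 = 0.25 and (11.95 − 4)/11.95 = 0.67
- At SD 0.4 the limits are 0.31 and 0.64; at SD 0.6 they are 0.19 and 0.69

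Five identical regimens at MGI 8 show a median spread of 0.23 in the index (0.18 to 0.27 over the same SDs).

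**The case against.** The strongest reply is that uncertainty is already in the plan. The GMT-ratio CI, the MGI CIs and the fever CIs will all be reported. D is driven mainly by D_GMT, so a reader can look for overlap in the planned intervals. Since (MGI − 4)/MGI rises steadily with MGI, its interval follows directly from the MGI limits. This stands as far as the components go. A reader might infer that the plan contains no measure of uncertainty, or that its results cannot be interpreted, and the documents do not support either. What remains is that none of this is carried to the ranked quantities, and the planned GMT-ratio intervals compare each alternative with the reference, not with another alternative.

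A second reply is that the ranking is descriptive. That is correct. A reader might infer that the order decides or steers the dose. But SAP 7.4 proposes no selection algorithm, and it also weighs other safety concerns and practical matters. The ranking informs the choice. The absence of an algorithm still leaves readers to judge how large a gap matters, which requires its precision.

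Third, a reader might infer that ranking on lower limits is the same as ranking on point estimates throughout. It is so only among the four alternatives. Over all five groups, ranked on D_GMT alone with identical regimens, the two orders agreed in only 17 to 20% of simulated trials, because the reference carries no penalty.

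**Conclusion.** The concern holds in limited form. D, the persistence index and the boostability index are ranked without any interval or rank uncertainty of their own, and the lower limit inside D_GMT does not show whether the four alternatives differ. A gap in D of about 0.17 between the best and worst alternative is what chance alone typically produces at SD 0.60. D also favours the reference by construction, and nothing in the ranking shows this.

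The sizes rest on 34 evaluable per group, the SD range of Table 21, a model without covariates, and assumed fever days and temperature that have little influence. The MGI figures rest on an assumed fold-rise SD. The gap weakens what the ranking can support; it does not invalidate the component analyses.

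**What to change.** - **SAP 6.1.2.1:** add a within-group bootstrap of children (for example 2,000 resamples) that refits the ANCOVA and recomputes D_GMT, D_R and D. Report a 95% interval for each alternative's D and for pairwise differences in D among the four alternatives, and rank probabilities among the alternatives.
- **Persistence and boostability:** transform the MGI 95% limits through (MGI − 4)/MGI, with 0 below MGI 4.
- **SAP 7.4:** state that alternatives whose difference-in-D interval includes 0 are reported as not distinguished. Also state that D favours the reference by construction.
- **Comparisons with the reference:** do not apply that rule here. Read them from the GMT-ratio 95% CI and from the difference in D_R with its own interval. In a simulated bootstrap with identical regimens and no covariates, the interval for alternative minus reference excluded 0 in about 61 to 67% of comparisons, against about 3 to 7% between alternatives. The rule would therefore usually declare a difference from the reference that does not exist.

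The cost is SAP wording, one program and one table. No endpoint, visit, sample size or treatment changes. Some rankings will be reported as inconclusive.
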